10	Observation status	
The number of follow-up examinations will be calculated by observation time point based on the actual status of follow-up examinations at the observation time point.
 
However, the following criteria should be followed for withdrawals.
 
 • In the case of withdrawal due to "inability to contact" the subject shall be assessed by identifying the time point of dropout based on the scheduled date * and observing the subject up to the previous time. 
However, if the contact is conducted at the relevant time point before "contact is not possible" is established, the observation shall be carried out until that time.
 
 • Other withdrawal dates will be the last follow -up date. 
However, "death" shall be specified based on the expected date. In addition, the time point for "other than death" should be specified after considering the range of adoption of the scheduled date.
 
 • Even if there are no dropouts on the questionnaire, if no follow -up is performed twice at 1 year or later, it is considered dropouts, and the date of first unsupervised follow-up (expected date) is considered the final observation (e.g., if 4-year and 5-year observations are not performed, 1460 days are considered the final observation date). 
※Expected date (scope of employment) 1 year: 365 days (365 ± 30 days) 2 years: 730 days (730 ± 30 days) 3 years: 1095 days (1095 ± 30 days) 4 years: 1460 days (1460 ± 30 days) 5 years: 1825 days (1825 ± 30 days)

11	Analysis set by time point	
The following conditions will be added to the observation status to identify the number of patients included in the analysis at each time point:
 
 • Cases in which death, myocardial infarction, or total revascularization occurred will be included in the analysis at all time points.

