Summary statistics (incidence)	
Incidence rates (%), number of events (molecules), number of populations analyzed (denominators) and 95% confidence intervals of frequencies are calculated. However, cases in which the relevant variable is a missing value are also included in the population of the incidence calculation.
 
4.3 Population numbers for antiplatelet therapy and 4.4 adverse events are specified as follows.
 
4.3 Antiplatelet therapy
 
Newly enrolled patients will be included.
 
Pre-procedure: Case of stenting
 
Procedure Day to Discharge Day: Stenting Cases
 
Procedural Day ~ 8 Months Observation Day: 8 Months Analyzed by Case Time Point of Stenting
 
Procedural Day-1 Year Observation Day: 1 Year Analyzed by Time Point of Stent Implantation
 
Procedural Day ~ 2 Years Observation Day: 2 Years Analyzed by Time Point of Stent Implantation
 
Procedural Day ~ 3 Years Observation Day: 3 Years Analyzed by Time Point of Stent Implantation
 
Procedural Day ~ 4 Years Observation Day: 4 Years Analysis Population by Time Point of Stent Implantation
 
Procedural Day ~ 5 Years Observation Day: 5 Years Analysis Population by Time Point of Stent Implantation
 
4.4 Adverse Events
 
Newly enrolled patients will be included.
 
Procedural Day + 3 Day: Stent Case
 
Procedural Day +4 Days or Beyond to Discharge Day: Stenting Cases
 
The day after discharge to the observation day of Month 8: 8 months for analysis by time point of stenting
 
Observation day of 8 months to 1 year: 1 year for analysis by time point of stenting
 
Observation day 1 to 2 years after the observation day of 1 year: 2 years for analysis by time point of stented patients
 
Observation day of 2-year observation day to 3-year observation day: 3 years for analysis by time point of stented patients
 
Observation day of the following day of observation in Year 3 to Year 4: 4 years for analysis by time point of stent implantation
 
Observation day of the following day of observation in Year 4 to Year 5: 5 years for analysis by time point of stenting
 
During hospitalization: patients with stents
 
Until 8 months: Stent implantation
 
Until 1 year: Stent implantation
 
Until 2 years: Cases of stenting
 
Until 3 years: Cases of stenting
 
Until 4 years: Cases of stenting
 
Until the end of the survey: patients undergoing stent placement
 
Overall post-procedure: stenting cases

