
Items	Calculation method, etc.
Confidence interval for the incidence	
Accurate confidence intervals based on Clopper-Pearson method will be calculated.
 $\pi_L = \frac{v_2}{v_2 + v_1 F_{\alpha/2}[v_1, v_2]} \quad v_1 = 2(n - x + 1), v_2 = 2x$ $\pi_U = \frac{v_1 F_{\alpha/2}[v_1, v_2]}{v_2 + v_1 F_{\alpha/2}[v_1, v_2]} \quad v_1 = 2(x + 1), v_2 = 2(n - x)$
Age (years)	The actual age at the date of the procedure (date of registration) is calculated from the date of birth (date is read in one day).
Body Mass Index	Calculated from weight (kg) and height (cm). Body Mass Index = Weight (kg)/ (Height (cm)/100) ²
Acceptable range on the observation day	
Observation day of 8 months: ± 30 days 8 months after the procedure day Observation day 1 year: ± 30 days after the procedure day Observation date of 2 years: ± 30 days 2 years after the procedure date Observation day 3 years: ± 30 days 3 years after the procedure date Observation day in Year 4: ± 30 days 4 years after the procedure date Observation day in 5 years: ± 30 days 5 years after the procedure date
 
However, if it can be confirmed that there is no problem with the data quality, it should be adopted as the data at the time according to the time of the questionnaire, even if it is outside the range.

4. Statistical Analysis Content

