4.4. Adverse Events

4.4.1. Adverse events (composite endpoint)

For adverse events (composite endpoint), incidence rates will be calculated by product for each time of onset.

No	Time of onset
1	Procedural day + 3 days from procedure date
2	Procedural Day + Day 4 or later to discharge date
3	Observation day of the day after discharge to Month 8
4	Observation day of Month 8 to Observation day of Year 1
5	Observation day of 1 year to the following day of 2 years
6	Observation day of the following day of Year 2 to Observation day of Year 3
7	Observation day of Year 3 to Year 4
8	Observation day following the observation day of Year 4 to the observation day of Year 5
9	During hospitalization
10	Up to 8 months
11	Until one year
12	Until 2 years
13	Up to 3 years
14	Up to 4 years
15	Until the end of the survey
16	Entire post-procedure

Table 18. Adverse events (composite endpoint, by time of onset)

- Analysis set: Stent implantation cases (newly enrolled patients)

Items [] indicating Breakdown

No	Item name
1	Target Lesion Failure [TLR Based on Cardiac Death, Myocardial Infarction Associated with Target Vessels, and Ischemic Findings].
2	Death + myocardial infarction + revascularization [death, myocardial infarction, revascularization]
3	Target vessel failure [cardiac death, myocardial infarction, TLR based on ischemic findings, TVR (non-TLR) based on ischemic findings, TVR (TLR or TVR (non-TLR)) based on ischemic findings].
4	Major adverse cardiac events (cardiac death, total myocardial infarction, TLR based on ischemic findings)
5	Death or myocardial infarction
6	Cardiac death or myocardial infarction
7	Myocardial infarction related to cardiac death or target vessel

Determination of myocardial infarction is based on the WHO (SPIRIT III) definitions

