4.4.4. Adverse events (survival time analysis)

Cumulative incidence is plotted by Kaplan-Meier for the AEs defined below, with the first occurrence as an event and non-occurrence as censored. In addition, the sample size, cumulative incidence, and 95% confidence interval of the cumulative incidence will be calculated for the at-risk population at 240, 365, 730, 1095, 1460, 1825 days, and the entire period.

Figure 21. Adverse events (by survival time analysis event)

- Analysis set: Stent implantation cases (newly enrolled patients)

No	Items	Definitions
1	Event	Death, TLR based on ischemic findings, first occurrence of stent thrombosis as event Use non-event cases as truncation examples
2	Survival time	Event example: Event date-Procedure date + 1 Censored: last contact date or withdrawal date-procedure date + 1

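### Cumulative MACE, TLF and TVF are planned only as crude proportions of all stented patients; SAP 4.4.4 should add a censoring-adjusted estimate

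*SAP*

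**What the plan says.** SAP 3.2 (summary statistics for incidence) sets the adverse-event denominators. The cumulative rows use all stented new patients throughout: at 1 year "Until 1 year: Stent implantation", and after the 4-year row "Until the end of the survey: patients undergoing stent placement". It adds that "cases in which the relevant variable is a missing value are also included in the population of the incidence calculation". Intervals are Clopper-Pearson.

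SAP 4.4.1 (Table 18) applies these rows to the composites, including "Major adverse cardiac events (cardiac death, total myocardial infarction, TLR based on ischemic findings", TLF and TVF. The only measure planned is an incidence rate per onset window.

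SAP 4.4.4 plans Kaplan-Meier estimates with 95% intervals for "Death, TLR based on ischemic findings, first occurrence of stent thrombosis as event", reported for the "at-risk population at 240, 365, 730, 1095, 1460, 1825 days, and the entire period". Patients without an event are censored at last contact or withdrawal.

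SAP 2.1, definition 10, expects losses. It has rules for patients who cannot be contacted and for two missed visits from year 1 onward. Definition 11 governs the single-period rows: "Cases in which death, myocardial infarction, or total revascularization occurred will be included in the analysis at all time points".

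**The concern.** A crude proportion of everyone stented is an unbiased cumulative risk only if no one is lost while still at risk. A patient last seen event-free at month 3 stays in the denominator at 1 and 4 years and can never enter the numerator.

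The rest of the plan does not fill the gap:

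- **Kaplan-Meier list.** Whether 4.4.4 means three curves or one combined event, it leaves out myocardial infarction and non-TLR target vessel revascularization. MACE, TLF and TVF cannot be obtained from it.
- **Single-period rows.** Each covers one period. Because definition 11 keeps patients with an earlier event in every later set, these rows are not conditional risks and cannot be chained into a cumulative one.

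The plan is therefore uneven: ischemia-based TLR gets a censoring-adjusted estimate at 365 days, while MACE, which contains it and on which the survey was sized, does not. At stake is a slightly optimistic MACE rate in the reexamination data, with the error growing on the later rows.

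**Working it through.** **The plan's own figure.** Clopper-Pearson for 45/300 gives 11.2% to 19.6%, a half-width of 4.2 points, or 28% of 15%. This reproduces Protocol 2.3 and SAP 1.3.

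**Inputs**
- From the documents: n = 300; 1-year MACE 15%.
- Assumed: dropout d = 2, 5 or 8% per year, exponential and independent of events.
- Assumed: after year 1, a fraction r of event-free patients has an event each year. The base value is 3% and the range 1-5%.

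**Formula.** Let l be the yearly event hazard (-ln 0.85 in year 1, then -ln(1-r)) and c = -ln(1-d). For each year the crude numerator gains

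S × G × l/(l+c) × (1 - exp(-(l+c))),

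where S and G are the probabilities of being event-free and still followed at the start of that year. Shortfall = true cumulative rate minus crude rate.

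**1 year**
- d = 2%: 0.16252/(0.16252+0.02020) × (1 - 0.85×0.98) = 0.8894 × 0.167 = 14.85%. Shortfall 0.15.
- d = 8%: 0.16252/(0.16252+0.08338) × (1 - 0.85×0.92) = 0.6609 × 0.218 = 14.41%. Shortfall 0.59.

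**4 years, r = 3%.** True rate 1 - 0.85×0.97³ = 22.42%.

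| Dropout per year | Crude, 1 year | Shortfall | Crude, 4 years | Shortfall |
|---|---|---|---|---|
| 2% | 14.85% | 0.15 | 21.92% | 0.51 |
| 5% | 14.63% | 0.37 | 21.18% | 1.25 |
| 8% | 14.41% | 0.59 | 20.46% | 1.96 |

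**Sensitivity to the later event rate (4 years, d = 2% to 8%).** r = 1%: 0.27-1.06 points. r = 5%: 0.73-2.82 points.

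**Sensitivity to timing of loss.** If patients lost during year 1 contribute no events at all in that year, the 1-year shortfall is 15% × d, or 0.30-1.20 points.

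**Competing death.** With non-cardiac death of 1-2% per year (assumed), the target falls to 14.85-14.93% at 1 year and 21.92-22.17% at 4 years. The crude shortfall against it is nearly unchanged: 0.14-0.59 and 0.49-1.92 points.

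**Against sampling error.** At 1 year, 0.59/4.2 is about 14% of the half-width. At 4 years (67/300, half-width 4.9), 1.96/4.9 is about 40%.

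**Does the censoring date matter?** Simulated at d = 8%, r = 3%, with visits at 8 months and then yearly. Censoring at the true dropout date removes the bias. Censoring at the first missed visit leaves a shortfall of about 0.3 points at 1 year and 0.6 at 4 years. Censoring at the last completed visit overstates by similar amounts.

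**The case against.** The survey is descriptive. MACE has no hypothesis, comparator or threshold, and Protocol 6.1 does not list it among the important evaluation items. Stent thrombosis, which is listed, already has Kaplan-Meier. The sizing is binomial, so a crude proportion matches the design. Loss is also restrained: Protocol 2.2 excludes patients known to be unable to return at 8 months and 1 year, Protocol 3 allows telephone contact at every yearly follow-up, Protocol 5.7 captures unscheduled visits with reportable events, and SAP Table 2 shows follow-up. Of the MACE components in Table 18, only infarction has no time-to-event estimate of any kind. All of this stands. It limits the importance of the point and makes the 8% end less likely.

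It is also fair to say that the remedy is not automatically unbiased. It assumes non-informative censoring. Definition 10 can place the final observation of an undeclared dropout at the expected date of a missed visit, after the last contact, and the documents do not say whether that date would reach the survival analysis. This is a reason to fix the date, not to omit the estimate.

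Three stronger readings should be resisted. A reader might infer that 1-year MACE is materially understated or that the 4.2-point precision fails; the 1-year shortfall does not support that. A reader might take the 4-year figure as a consequence of dropout alone; it also needs a later event rate that neither document gives. A reader might carry the figures over to TLF and TVF; the documents give an expected rate only for MACE.

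**Conclusion.** The structural point is certain from the text: no censoring-adjusted estimate of MACE, TLF or TVF is planned. The direction of the bias follows whenever anyone is lost while at risk. The size is conditional, for MACE only: roughly 0.15-0.6 points at 1 year, resting on the documents' 15% and an assumed 2-8% yearly independent dropout; and at 4 years 0.5-2.0 points with an assumed 3% later yearly event rate, or 0.3-2.8 points across 1-5%. This is a cheap improvement to reporting. It does not threaten the survey's conclusions.

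**What to change.** **Change**
1. Add MACE, TLF and TVF to the SAP 4.4.4 list at days 240, 365, 730, 1095, 1460 and 1825, with 95% confidence intervals.
2. Use a cumulative incidence function, treating death not counted in the composite as a competing event. If ischemia-based TLR stays on plain Kaplan-Meier, say in a footnote that the estimators differ.
3. Censor at the last contact or withdrawal date already defined in 4.4.4, and state that the expected-date rule in definition 10 does not set the censoring date. Record last contact as the latest date on which event status is known. If it is only the last completed visit, the small overstatement shown in the working applies.
4. Keep the crude proportion alongside, with the number of patients followed to that day.
5. Do not change the denominator to patients with an event or complete follow-up. With r = 3% and 2-8% dropout, that reads 15.1-15.6% at 1 year and 23.4-26.9% at 4 years, against true rates of 15.0% and 22.4%.

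**Cost.** SAP wording and a few more runs on data already collected. Reported rates become slightly higher. Simulated 95% half-widths (n = 300, dropout 2-8%, non-cardiac death 1-2% per year) for the cumulative incidence function against Clopper-Pearson are 4.0-4.1 against 4.1-4.2 points at 1 year, and 4.7-5.0 against 4.7-4.8 at 4 years. Late intervals therefore widen slightly, and the estimate relies on non-informative censoring, which the SAP should state.

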4.1. SUMMARY OF SURVEY AND CASE STRUCTURE

- Analysis set: Cases collected by questionnaire

4.1.1. Number of patients at each center

The number of patients collected by questionnaire, the number of patients not covered by the survey, the number of patients surveyed, the number of patients not stented, and the number of patients stented will be tabulated. In addition, the corresponding case number is indicated for cases not covered by the survey and cases not covered by the stent.

Figure 1. Case structure

- Analysis set: Cases collected by questionnaire

4.1.2. Number of patients at each center

The number of patients collected by institution, the number of patients surveyed, and the number of stented patients will be tabulated.

Table 1. Number of patients by center

- Analysis set: Cases collected by questionnaire

4.1.3. Observation status

Follow-up by booklet and the number of patients included in the analysis by time point will be tabulated.

Table 2. Conduct of follow-up examinations

- Subjects for analysis: Subjects for investigation

4.1.4. Status at the end of the survey

The status at the end of the survey is tabulated.

Table 3. Status at the end of the survey

- Analysis set: Stent implantation cases

4.1.5. Ischemic findings at enrollment

For ischemic findings at the time of enrollment specified below, the proportion and confidence interval of relevant cases will be calculated.

Table 4. Ischemic findings at enrollment

- Analysis set: Stent implantation cases (newly enrolled patients)

Items: [] indicating Breakdown

No	Item name
1	Acute myocardial infarction [ST-segment elevation myocardial infarction, non-ST-segment elevation myocardial infarction]

No	Item name
2	Unstable Angina [Branwold Classification: Class I to Class III].
3	Stable angina pectoris [CCS Angina Classification: Class I to Class IV].
4	Silent ischemia
5	Old myocardial infarction (no evidence of ischemia)
6	Coronary stenosis (no evidence of ischemia)

4.1.6. Basic demographic information

Summary statistics of the basic demographic information specified below or proportions and confidence intervals of relevant cases will be calculated.

Table 5. Basic demographic information

- Analysis set: Stent implantation cases (newly enrolled patients)

Items * calculate summary statistics

No	Item name
1*	Age (years)
2	Age 75 years or older
3	Sex at birth (male, female)
4*	Height (cm)
5*	Body weight (kg)
6*	Body Mass Index (kg/ m ²)
7	Body Mass Index: Less than 18.5kg/m ² Body Mass Index: 18.5kg/m ² or more, less than 25kg/m ² Body Mass Index: 25kg/m ² or more, less than 30kg/m ² Body Mass Index: 30kg/m ² or more, less than 35kg/m ² Body Mass Index: 35kg/m ² or more, less than 40kg/m ² Body Mass Index: 40kg/m ² or higher

4.1.7. Risk Factors and History

The proportion and confidence interval of relevant cases will be calculated for the risk factors and medical history specified below.

Table 6 Risk Factors and History

- Analysis set: Stent implantation cases (newly enrolled patients)

Items [] indicating Breakdown

No	Item name
1	LVEF < 30%
2	History of myocardial infarction
3	History of CABG
4	History of PCI
5	Family History of Juvenile Coronary Artery Disease
6	Current smoking or cessation within the past month
7	Hypertension [requiring pharmacotherapy, not requiring pharmacotherapy]
8	Dyslipidemia [requiring pharmacotherapy, not requiring pharmacotherapy]
9	Renal failure (kidney disease) History [introdialytic, end-stage renal failure (eGFR < 30 mL/min/1.73m ²), chronic kidney disease (eGFR < 60 mL/min/1.73m ²)]
10	History of stroke
11	History of serious bleeding

No	Item name
12	History of unstable arrhythmia
13	Anticoagulant therapy

4.1.8. History of diabetes

The percentage and confidence interval of relevant cases will be calculated for the history of diabetes mellitus specified below.

Table 7. History of diabetes mellitus

- Analysis set: Stent implantation cases (newly enrolled patients)

Items [] indicating Breakdown

No	Item name
1	History of diabetes mellitus [type 1 diabetes mellitus, type 2 diabetes mellitus]
2	History of diabetes mellitus requiring pharmacotherapy [insulin therapy, oral antidiabetic drug treatment]

4.2. Lesions and Techniques

4.2.1. Information on treated lesions

Summary statistics or percentages and confidence intervals of relevant cases will be calculated for the information on the treated lesions specified below.

Table 8-1 Information on treated lesions (main branches for bifurcation lesions)

- Analysis set: Stent implantation cases (newly enrolled patients)

Items * calculate summary statistics

No	Item name
1*	Number of target lesions per patient
2	Number of target lesions per patient 1 lesion
3	Target number of lesions per patient 2 lesions
4	Target number of lesions per patient 3 lesions
5	Number of target lesions per patient ≥ 4 lesions
6	Lesion type new lesion
7	Lesion-type stent restenosis
8	Restenosis other than lesion-type stent treatment
9	Lesion type, etc.

Table 8-2 Location of target lesions (branches, main branches)

- Analysis set: Stent implantation cases (newly enrolled patients)

Items [] indicating Breakdown

No	Item name
1	Autologous coronary artery [LMT [protected, unprotected], RCA, LAD, LCX]
2	SVG
3	Arterial graft

Table 8-3. AHA segments (branches, main branches) of target lesions

- Analysis set: Stent implantation cases (newly enrolled patients)

Items

No	Item name
1	AHA-1 - AHA-15

Table 8-4. Presence of complex lesions

- Analysis set: Stent implantation cases (newly enrolled patients)

Items

No	Item name
1	Complex lesion bifurcation lesion
2	Complex lesion ST-elevation myocardial infarction culprit lesion
3	Complex lesion chronic total occlusion (CTO) lesions.
4	Complex lesion entrance lesion (less than 3mm from the aortic inlet or LAD/LCX bifurcation)
5	Complex lesion hypermineralization
6	Thrombi within complex lesion-treated vessels
7	Complex lesion or proximal flexion >90 degrees
8	Complex lesion or excessive tortuosity of the proximal segment
9	Complex lesions, etc.

4.2.2. Treatment Lesion Stenosis Evaluation (All Lesions, Evaluated by Institution)

Summary statistics for preprocedural lesion length (mm) are calculated. Also, summary statistics for pre-procedure vessel diameter (mm) and %DS will be calculated by product.

Table 9. Target lesion stenosis assessment (all lesions, assessed by center)

- Analysis set: Stent implantation cases (newly enrolled patients)

4.2.3. Procedural Information-General Information

Summary statistics or percentages and confidence intervals of relevant cases will be calculated by product for procedural information specified below.

TABLE 10 PROCEDURES INFORMATION-GENERAL INFORMATION

- Analysis set: Stent implantation cases (newly enrolled patients)

Items * calculate summary statistics

No	Item name
1	Access site femoral artery
2	Access site radial artery
3	Access site brachial artery
4	Access site, etc.
5*	Number of care lesions per patient
6*	Number of target lesions per patient
7*	Number of lesions treated with XP_SV only Mean, standard deviation and sample size only calculated
8*	Mean number of lesions treated with XP_SV combined with other stents,

No	Item name
	standard deviation and sample size only calculated
9*	Number of non-target lesions Mean, standard deviation and sample size only calculated
10*	Total number of stents placed per patient
11*	Total length of stent placed per patient (mm)
12*	Time (min) required for the procedure

